6 STUDY VARIABLES AND METHODS OF ASSESSMENT

6.1 Determination of Optimum Dose

Part 1 of the study is designed with co-primary endpoints of efficacy and tolerability, in order to facilitate dose selection for further investigation. Data from Part 1 of this Phase IIA study will be reviewed in its totality to provide an understanding of the dose-response relationship, both in terms of efficacy and tolerability, in order to determine an optimum dose for further development in Part 2.

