2.1 Overall Study Design

This study is designed as a multicenter, single arm, non-randomized phase IIA study to evaluate ASLAN003 as a monotherapy in patients with AML.

AML patients who are ineligible for standard treatment including, but not limited to the following conditions, will be enrolled in the study:

- Newly diagnosed patients who are ineligible for standard therapy i.e., standard dose induction chemotherapy and reduced dose chemotherapy
- Patients with relapse from prior remission
- Patients with failed response to prior therapy including chemotherapy, hypomethylating agents, and bone marrow transplantation.

[figure not shown]
Part 1:

Up to a total of 24 patients will be enrolled into Part 1 of this study – 6 patients in each dose cohort (ASLAN003 100 mg once daily (QD), 200 mg QD, 100 mg twice daily (BID) and 200 mg BID, respectively). Once 6 patients have been enrolled into the cohort of 100 mg QD, recruitment will be started in the cohort of 200 mg QD. The same rule applies to the 100 mg BID and 200 mg BID cohorts. A steering committee (SC) meeting will be set up and meet to review all safety data. Details of the SC outcome will be specified in the SC charter.

Part 2:

An expansion cohort of 20 patients will be recruited to study the optimum dose selected by the SC. The optimum dose will be selected from at least one cohort showing tolerable safety profile and clinical benefit in disease presentation. Details will be specified in the SC charter.

Figure 1: Study Design

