3.2 Safety and Tolerability

3.2.1 Safety Endpoints

The assessment of safety and tolerability is a co-primary objective of Part 1, and a secondary endpoint of Part 2. In both study parts, the safety and tolerability of ASLAN003, in AML patients, will be assessed using the following endpoints:

- Adverse Events (AEs)
- Physical Examination
- Vital Signs (blood pressure [systolic and diastolic], heart rate, respiration rate, and body temperature)
- Laboratory assessments (clinical chemistry, hematology, coagulation and urinalysis)
- 12-lead Electrocardiogram (ECG) (P and QRS duration, RR, PQ, QT and QTc intervals using Bazett's and Fridericia's formulae)
- Treatment exposure and dose intensity

In addition, tolerability will be further explored by assessment of dose reductions, interruptions and modifications (see Section 3.2.2).

Adverse events will be coded by System Organ Class (SOC) and Preferred Term (PT) using the Medical Dictionary for Regulatory Activities (MedDRA) for concomitant diseases and AEs and World Health Organization (WHO) Drug for medications. All AEs will be evaluated for severity according to NCI-CTCAE version 4.03

Baseline will be defined as the last assessment prior to the start of study treatment. If multiple assessments are performed at the same pre-treatment timepoint, for example triplicate ECG assessments, the mean of the values will be used as the baseline reading.

Creatinine clearance will be derived as:

$$eC_{Cr} = \frac{(140 - Age) \times Mass \text{ (in kilograms)} \times Constant}{Serum Creatinine \text{ (in } \mu\text{mol/L)}}$$

where constant=1.23 for males and 1.04 for females, and will be categorized as 30-
<60 ml/min, 60-<90 ml/min and =>90 ml/min. Creatinine clearance will be included in summaries of the clinical chemistry data.

QTcB will be derived as:

$$QTcB = \frac{QT}{\sqrt{RR}}$$

QTcF will be derived as:

$$QTcF = \frac{QT}{\sqrt[3]{RR}}$$

For derivation of post-baseline visit values, taking account of possible visit windows, see Section 3.2.1.1.

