6.1 Sample Size Estimation

This Phase IIA study is not formally powered.

6.1.1 Part 1

For Part 1, the proposed design of up to 6 patients per dose level has been selected to provide an assessment of the safety, tolerability and efficacy of up to 3 dose levels of ASLAN003, in order to select the most appropriate dose for further exploration in Part 2.

6.1.2 Part 2

The sample size of 20 patients for Part 2 has been selected to provide further efficacy and tolerability data at the selected dose level from Part 1, prior to conducting larger randomized trials in AML.

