7.7 Assessment of Safety and Tolerability

7.7.1 Assessment of Safety

All safety data will be assessed for the safety population.

All AE data will be listed along with information regarding initial study dose, dose at onset, onset time, duration, severity, and relationship to study treatment.

Treatment emergent AEs (TEAEs) are defined as AEs with an onset date on or after the start of treatment. The following summaries will be produced for both study parts, by dose group and overall for Part 1, for all TEAEs:

- An overview table of the incidence of TEAEs, grade 3+ TEAEs, SAEs, TEAEs leading to treatment discontinuation and TEAEs leading to death. For each summary category, the results will be shown overall (regardless of causality), and for the incidence of causally related TEAEs. For example, the overall incidence of TEAEs will be presented, as well as the incidence of TEAEs classified as at least possibly related to ASLAN003 by the Investigator.
- Summary of TEAEs by SOC and PT: Both the number and percentage of patients in each category (patient-level summary) and the number of episodes (episode-level summary). This summary table will be repeated for TEAEs attributed as causally related to study treatment.
- Summary of TEAEs, sorted in descending order of frequency (i.e. most frequent event shown first) presented by dose group (Part 1 only) and overall. The order of frequency will be determined by the most frequent preferred term overall. For each event, the results will be presented for all CTC grades, and also split by grade 1-2, and grade 3+.
- Summary of TEAEs attributed as causally related to study treatment, sorted in descending order of frequency (i.e. most frequent event shown first) presented by dose group (Part 1 only) and overall. The order of frequency will be determined by the most frequent preferred term overall. For each event, the results will be presented for all CTC grades, and also split by grade 1-2, and grade 3+.

- Summary of CTC grade 3 and above TEAEs sorted in descending order of frequency (i.e. most frequent event shown first). The order of frequency will be determined by the most frequent preferred term overall. Results will be presented by dose group (Part 1) and overall.

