- For all continuous data except the haematological parameters, box plots of the change from baseline over time, by dose group (Part 1), including a horizontal reference line at zero
- For haematological parameters, box plots of the absolute values over time, by dose group (Part 1), including a horizontal reference line at zero

To enable assessment of the potential for drug-induced liver injury, for all study parts the following outputs will be produced:

- A scatter plot of maximum on-treatment alanine aminotransferase (ALT) versus maximum on-treatment total bilirubin (x-axis), both expressed as multiples of the ULN, including reference lines at $3 \times \text{ULN}$ for ALT, and $2 \times \text{ULN}$ for total bilirubin. For each patient, the maximum ALT and maximum total bilirubin may occur at different visits
- A scatter plot of maximum on-treatment aspartate aminotransferase (AST) versus maximum on-treatment total bilirubin (x-axis), both expressed as multiples of the ULN, including reference lines at $3 \times \text{ULN}$ for AST, and $2 \times \text{ULN}$ for total bilirubin. For each patient, the maximum AST and maximum total bilirubin may occur at different visits.

In the event that the scatter plots of ALT or AST against bilirubin identify any potential Hy's law cases (patients with either both $\text{ALT} > 3 \times \text{ULN}$ and total bilirubin $> 2 \times \text{ULN}$, or both $\text{AST} > 3 \times \text{ULN}$ and total bilirubin $> 2 \times \text{ULN}$), profile plots over time will be produced for these patient's liver function tests (ALT, AST, ALP and total bilirubin), expressed in multiples of the ULN, showing all four FLT parameters on the same plot.

Physical examination data will be listed.

To further assess the tolerability of ASLAN003, dose intensity and treatment exposure, as defined in Section 3.2.2, will be listed and summarized by treatment arm. Dose intensity and exposure summaries will be presented by cycle for the first 3 cycles, and overall.

Swimmer plots of the time on treatment will be presented for all patients in the EFR set. The bars on these plots will be ordered as follows:

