9. LIST OF TABLES, FIGURES AND LISTINGS

9.1 Tables

Unless otherwise stated, tables will be all repeated for part 1 and part 2.

Table Number	Table Title
14.1.1	Patient Disposition and Withdrawals – All Patients
14.1.2	Analysis Populations – All Patients
14.1.3.1	Major Protocol Deviations – Full Analysis Set
14.1.3.2	Other Important Protocol Deviations – Full Analysis Set
14.1.4	Demographic Characteristics – Full Analysis Set
14.1.5	Prior Therapies for AML – Full Analysis Set
14.2.1.1	Summary of Overall Complete Remission Rate – EFR Population
14.2.1.2	Summary of Overall Complete Remission Rate – Full Analysis Set
14.2.2.1	Summary Statistics for Relapse-Free Survival – EFR Population
14.2.2.2	Summary Statistics for Relapse-Free Survival – Full Analysis Set
14.2.3.1	Summary of Clinical Benefit Rate – EFR Population
14.2.3.2	Summary of Clinical Benefit Rate – Full Analysis Set
14.2.5.1	Summary of Plasma Concentrations – ASLAN003 – PK Population
14.2.5.2	Summary of Plasma Concentrations – LAS186558 – PK Population
14.2.5.3	Summary of Plasma Pharmacokinetic Parameters – ASLAN003 - PK Population
14.2.5.4	Summary of Plasma Pharmacokinetic Parameters – LAS186558 - PK Population
14.3.1.1	Summary Statistics for Exposure – Safety Population
14.3.1.2	Summary Statistics for Dose Intensity – Safety Population
14.3.2.1	Overview of TEAEs – Safety Population

Table Number	Table Title
14.3.2.2	Incidence of TEAEs by System Organ Class and Preferred Term – Patient and Episode Level – Safety Population
14.3.2.3	Incidence of Causally Related TEAEs by System Organ Class and Preferred Term – Patient and Episode Level – Safety Population
14.3.2.4	Incidence of most frequent (>10%) TEAEs by Preferred Term – Safety Population
14.3.2.5	Incidence of most frequent (>10%) Causally Related TEAEs by Preferred Term – Safety Population
14.3.2.6	Incidence of TEAEs CTCAE Grade 3 or Higher by System Organ Class and Preferred Term – Safety Population
14.3.2.7	Incidence of Causally Related TEAEs CTCAE Grade 3 or Higher by System Organ Class and Preferred Term – Safety Population
14.3.2.8	Incidence of Serious TEAEs by System Organ Class and Preferred Term – Safety Population
14.3.2.9	Incidence of Serious Causally Related TEAEs by System Organ Class and Preferred Term – Safety Population
14.3.3	Summary of Deaths – Safety Population

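### Part 1 tabulates adverse events by dose cohort as crude incidence over unequal time at risk, and no planned AE table allows for the difference

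*SAP*

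**What the plan says.** SAP 7.7.1 produces the Part 1 TEAE summaries by dose group and overall, beginning with "An overview table of the incidence of TEAEs, grade 3+ TEAEs, SAEs, TEAEs leading to treatment discontinuation and TEAEs leading to death". The Grade 3+ table in SAP 9.1 (14.3.2.6) has the same form: "Incidence of TEAEs CTCAE Grade 3 or Higher by System Organ Class and Preferred Term". The SOC/PT tables give numbers and percentages of patients plus raw episode counts. An event reported more than once is shown at its worst grade over the study. Events starting more than 28 days after stopping drug are left out of the tables. SAP 4.1 assigns each patient to the dose first received, whatever happens later.

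Time on drug is not fixed. Under Protocol 3.4, treatment runs until relapse, treatment failure (no PR or better within 4 cycles), unacceptable toxicity, consent withdrawal or death.

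These tables feed a primary purpose of Part 1. SAP 3.2.1 states: "The assessment of safety and tolerability is a co-primary objective of Part 1". On the dose choice, Protocol 6.1 says: "Data from Part 1 of this Phase IIA study will be reviewed in its totality to provide an understanding of the dose-response relationship".

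For drug exposure the SAP does split time: "Dose intensity and exposure summaries will be presented by cycle for the first 3 cycles, and overall". Neither SAP 7.7.1 nor SAP 9.1 contains a matching AE table for a common window, an AE rate per unit of patient time, or a time-to-first-event summary.

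**The concern.** A crude percentage of patients ever affected rises with time observed, even when risk per cycle does not change. Here the observation time depends partly on efficacy. A dose that produces remissions keeps its responders on drug for many cycles. A dose that fails loses its patients by about cycle 4 or sooner. Placed side by side, the crude percentages mix toxicity with duration, and the more active dose can look less tolerable than it is. The reverse can also happen: a cohort whose patients stop early for toxicity has less time to show later events. What is at stake is how the tolerability half of the dose selection for Part 2 is read.

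**Working it through.** The documents give no AE rate, no expected time on drug and no power figure ("This Phase IIA study is not formally powered"), so there is no planned figure to reproduce. What follows illustrates size under stated assumptions.

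**Inputs from the documents.** Cohort size: "6 patients in each dose cohort" (SAP 2.1). One cycle is 28 days (Protocol 3.4). The AE window is time on drug plus 28 days, which is cycles on drug plus 1 (SAP 7.7.1).

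**Assumptions.** The hazard h of a first Grade 3+ event per cycle is the same in both cohorts, so there is no dose effect. Times on drug are illustrative.

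**Formula.** Expected incidence = 1 − exp(−h × window).

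1. *Uniform time on drug, h = 0.2, 1.5 versus 4 cycles.* The windows are 2.5 and 5 cycles.
   - Short cohort: 1 − exp(−0.5) = 39%, or 6 × 0.393 = 2.4 patients.
   - Long cohort: 1 − exp(−1.0) = 63%, or 6 × 0.632 = 3.8 patients.
   - Gap: about 1.4 patients.

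2. *The same mean of 4 cycles, produced by a few responders.* Take non-responders at 1.5 cycles and responders at 12.
   - The responder share r solves 1.5 + 10.5r = 4, so r = 0.238.
   - Responder incidence is 1 − exp(−0.2 × 13) = 92.6%.
   - Cohort incidence is 0.762 × 0.393 + 0.238 × 0.926 = 52%.
   - Against 39% in the short cohort, the gap is 6 × 0.127 = 0.8 of a patient. It is smaller than in step 1 because the incidence curve flattens with time, so a cohort mean put into the formula overstates the effect.

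3. *Front-loaded toxicity.* Take a hazard of 0.30 in Cycle 1 and 0.03 per cycle afterwards, including the 28-day tail.
   - 2 cycles on drug: 1 − exp(−0.36) = 30%.
   - 4 cycles: 1 − exp(−0.42) = 34%.
   - Gap: 6 × 0.041 = 0.24 of a patient. The direction is unchanged, but the size is small.

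4. *Set against chance.* For constant hazards of 0.05, 0.10, 0.20 and 0.40, treat the affected patients in each cohort as binomial with n = 6. Sum the exact probabilities that one named cohort shows at least 2 more affected patients than the other.

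| h per cycle | 2 vs 4 cycles (excess in the longer) | both 2 cycles | Cycle 1 only |
|---|---|---|---|
| 0.05 | 22% | 10% | 2% |
| 0.10 | 34% | 16% | 6% |
| 0.20 | 41% | 19% | 12% |
| 0.40 | 36% | 17% | 18% |

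Unequal time roughly doubles the chance of a misleading excess of 2. Chance alone is not negligible with 6 per cohort. In a Cycle 1 table both cohorts have the same expectation (for example 1 − exp(−0.2) = 18% at h = 0.2), apart from patients who leave within Cycle 1.

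**The case against.** The strongest reply is that nothing in the plan makes these percentages the decision metric. The analysis is descriptive, and the dose is a steering committee judgement: "Data from Part 1 of this Phase IIA study will be reviewed in its totality", with details left to a charter that is not among these documents. Much of the time dimension is already visible. AE listings carry onset time and dose at onset, exposure and dose intensity are themselves tolerability endpoints, and swimmer plots show each patient's time on treatment by response. With 6 patients per cohort, a careful reader can set onset against time on drug patient by patient. All of this stands, and it limits the weight of the point. What remains is that none of these displays puts the between-cohort AE percentages on equal time.

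Four stronger readings are tempting, and the documents do not carry them.

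- *The dose choice would be misled.* This cannot be shown, because there is no numeric selection rule and the charter's content is unknown.
- *The illustration could be 26% versus 55%.* Those are the values for 1.5 and 4 cycles at h = 0.2 if only time on drug counts (1 − exp(−0.3) and 1 − exp(−0.8)). SAP 7.7.1 also counts the 28 days after stopping, so 39% versus 63% is the consistent pair, and even that takes every patient at the cohort mean.
- *Sequential enrolment gives earlier cohorts longer exposure.* This needs a cut-off at which early-cohort patients are still on drug. The documents give no date for one, and SAP 6.4.2 plans no interim analysis.
- *The Cycle 1 halt provision in Protocol 6.3.1.6 makes Cycle 1 the right sole comparison.* That provision counts only clinically significant reactions rated probably or definitely related. It is a trigger for halting recruitment and does not compare cohorts. Treatment is continuous, so later toxicity matters too.

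**Conclusion.** The point holds as a shortcoming of presentation in a co-primary assessment. Part 1 AE incidence is crude, time at risk depends on response, and no planned AE table corrects for this. The direction is predictable when hazards are equal: the longer-treated cohort shows more affected patients. The size is not known. Under the assumptions above, the spurious gap runs from about a quarter of a patient in 6 (front-loaded toxicity, 2 versus 4 cycles), through 0.8 (a few long-treated responders), to 1.4 (constant hazard of 0.2, uniform 1.5 versus 4 cycles). The documents supply neither the hazard shape nor the times on drug, and larger differences in time on drug would widen the gap. The case for a change rests on its low cost and on the role of tolerability in dose selection.

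**What to change.** In SAP 7.7.1 and 9.1, add for Part 1, by dose cohort:

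- versions of Tables 14.3.2.1, 14.3.2.6 and 14.3.2.7 limited to Cycle 1 (Days 1–28);
- first-event rates per patient-cycle at risk for the same categories, with each patient's time ending at the first event or the end of the AE window, and total exposure shown in the same table.

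Present these beside the whole-period tables, which should stay so that late toxicity remains visible. Do not make Cycle 1 the only between-cohort comparison. State that every dosed patient stays in the Cycle 1 denominator, since Protocol 4.3 rules out replacement only after Cycle 1 is completed.

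The cost is a few extra tables from onset and dosing dates already collected. The limits should be stated with them. Cycle 1 tables miss late events. Early deaths and withdrawals leave some imbalance within Cycle 1. A rate per patient-cycle summarises risk well only if the hazard is roughly constant. With 6 patients per cohort, every estimate stays imprecise.

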7.8 Disposition of Patients

Patient disposition, including but not limited to, the date of informed consent, date of first dose and reasons for discontinuation from study treatment, will be listed and summarized by treatment group.

7.9 Demographics and Baseline Characteristics

Demographic and baseline characteristic data will be presented based on the FAS.

Baseline demographic data, including, but not limited to:

- age (as derived on the CRF)
- gender

- weight
- height
- race
- ethnicity

will be listed and summarized using appropriate descriptive statistics.

7.10 Medical History and Prior and Concomitant Medications

Relevant medical history and prior treatment for AML will be listed. Prior therapies will also be summarized by dose group (Part 1 only), type of therapy (induction, consolidation, salvage, maintenance or conditioning prior to transplant) and for the most recent therapy only, the response classification.

All medications received following the start of treatment (including those that were ongoing prior to first dose) will be listed.

Medications will be presented for the Safety population and coded using WHO Drug dictionary.

Frequency and percentage of concomitant medications use will be presented by Anatomical Therapeutic Chemical (ATC) level 2 and preferred name. Tables will also show the Total number and percentage of subjects receiving at least one treatment of a particular preferred name. Subjects receiving multiple medications within the same preferred names will be counted only once under that preferred name. Classification of Prior and concomitant medications will be based on medications start date and stop date as entered in prior and concomitant medications page of eCRF.

- 'Prior' medications are medications which started and stopped prior to the first capsule of study drug
- 'Concomitant' medications are medications which:
 - started prior to, on or after the first capsule of study drug and started before the end of study drug, and ended on or after the date of first dose of study drug or were ongoing at the end of the study drug
- 'Post treatment' medications are medications which are started after the last capsule of study drug and at or before the follow up visit

Concomitant medications will be summarised by ATC level 2 and preferred term based on Safety population.

7.11 Pharmacokinetic Analysis

The determination of the plasma concentration data will be performed at CPR Pharma Services using validated methods. The analytical methods will be conducted according to CPR Standard Operating Procedures (SOPs) for PK analyses unless otherwise specified.

Computation of pharmacokinetic parameters will be the responsibility of the pharmacokineticist at IQVIA, Overland Park, Kansas. The PK summaries, data listings,

and figures as well as the statistical analysis of the PK parameters will be the responsibility of the study biostatistician at IQVIA.

Standard non-compartmental methods with Phoenix® WinNonlin® 8.0 or higher (Certara, L.P., Princeton, New Jersey, US) or SAS® Version 9.2 or higher (SAS Institute, Inc., Cary, North Carolina, US). Actual elapsed time from dosing will be used for final plasma PK parameter calculations.

The pharmacokinetic analysis will be performed on the PK population after database lock following Part 1 of the study.

Where possible the following PK parameters will be determined for ASLAN003 and LAS186558 following single dose on Day 1.

- C_{max} Maximum plasma concentration (ng/mL) obtained directly from the observed concentration versus time data
- AUC_{last} Area under the plasma concentration-time curve from 0 to the time of the last quantifiable concentration (ng*h/mL), calculated by linear up/log down trapezoidal summation
- AUC_{tau} Area under the plasma concentration-time curve during the dosing interval, tau, (ng*h/mL), calculated by linear up/log down trapezoidal summation
- AUC_{inf} Area under the plasma concentration-time curve from time zero (pre-dose) extrapolated to infinity (ng*h/mL) calculated by linear up/log down trapezoidal summation and extrapolated to infinity by the addition of the last quantifiable concentration divided by the terminal rate constant: $AUC_{0-t} + C_{last}/\lambda_z$
- t_{max} Time to maximum plasma concentration (h) obtained directly from the observed concentration versus time data
- CL/F Apparent plasma clearance for ASLAN003 only (L/h), estimated as dose divided by AUC_{inf}
- V_z/F Apparent volume of distribution for ASLAN003 only (L), estimated by dividing the apparent clearance by λ_z
- λ_z Terminal rate constant (1/h) estimated by log-linear least-squares regression of the terminal part of the concentration-time curve
- $t_{1/2}$ Terminal elimination half-life (h). Visual assessment will be used to identify the terminal linear phase of the concentration-time profile

- MR Metabolite to parent ratio (LAS186558 to ASLAN003) for AUC_{τ} and C_{\max} ($MRAUC_{\tau}$ and MRC_{\max})
- C_{\max}/D Dose-normalized C_{\max} (ng/mL/mg).
- AUC_{last}/D Dose-normalized AUC_{last} (ng.h/mL/mg).
- AUC_{τ}/D Dose-normalized AUC_{τ} (ng.h/mL/mg).

The following PK parameters will be calculated for ASLAN003 and LAS186558 for diagnostic purposes and listed but not summarized:

- λ_z , Interval The time interval (h) of the log-linear regression to determine $t_{1/2}$
- λ_z , N Number of data points included in the log-linear regression analysis
- Rsq(adj) Coefficient of determination for calculation of λ_z . A value of >0.800 is indicative of good correlation and will be used as the criteria for reliable estimations of λ_z , $t_{1/2}$, and related parameters will not be reported if Rsq(adj) is ≤ 0.8
- %AUC Percentage of AUC obtained by extrapolation, calculated as $[(C_{\text{last}}/\lambda_z)/AUC_{\text{inf}}*100]$. If value is $>20\%$, AUC_{inf} , CL/F , and V_z/F will be listed but not included in any summaries or inferential analyses.

Where possible the following PK parameters will be determined for ASLAN003 and LAS186558 following multiple dosing on Day 8.

- $AUC_{\tau \text{ ss}}$ Area under the plasma concentration-time curve during the dosing interval, tau, (ng*h/mL), calculated by linear up/log down trapezoidal summation
- $C_{\max \text{ ss}}$ Maximum plasma concentration (ng/mL) obtained directly from the observed concentration versus time data
- $t_{\max \text{ ss}}$ Time to maximum plasma concentration (h) obtained directly from the observed concentration versus time data
- $AUC_{\text{last ss}}$ Area under the plasma concentration-time curve from 0 to the time of the last quantifiable concentration (ng*h/mL), calculated by linear up/log down trapezoidal summation

- C_{trough} Plasma concentration obtained prior to dosing on Day 8
- $t_{1/2 \text{ eff}}$ Effective elimination half-life at steady state calculated as
 $\ln 2 / \text{Lambda}_z \text{ (eff)} = [-\ln 2 * \tau / \ln \{1 - [AUC_{\tau, \text{ Day 1}} / AUC_{\tau, \text{ Day 8}}]\}]$ with
 $\tau = 24$ hours for QD dosing and 12 hours for BID dosing
- CL_{ss}/F Apparent plasma clearance for ASLAN003 only (L/h), estimated as dose divided by $AUC_{\tau \text{ ss}}$
- MR Metabolite to parent ratio (LAS186558 to ASLAN003) for $AUC_{\tau \text{ ss}}$ and $C_{\text{max ss}}$, ($MRAUC_{\tau \text{ ss}}$ and $MRC_{\text{max ss}}$)
- RacAUC Accumulation ratio for AUC calculated as $AUC_{\tau \text{ ss}}/AUC_{\tau}$ or $AUC_{\text{last ss}}/AUC_{\text{last}}$
- RacCmax Accumulation ratio for C_{max} calculated as $C_{\text{max ss}}/C_{\text{max}}$
- $C_{\text{max ss}}/D$ Dose-normalized $C_{\text{max ss}}$ (ng/mL/mg).
- $AUC_{\text{last ss}}/D$ Dose-normalized $AUC_{\text{last ss}}$ (ng.h/mL/mg).
- $AUC_{\tau \text{ ss}}/D$ Dose-normalized $AUC_{\tau \text{ ss}}$ (ng.h/mL/mg).

